#### **Uninsured Patients (5/8/2019):**

An Internal Medicine Consultant will be utilized as an advisor when complex medical non-neurologic issues arise for patients who do not yet have a primary care provider. The consultant will join the telehealth visits as appropriate to provide recommendations for management of complex medical issues that can be managed in the ambulatory setting.

#### **Usual Care (Control) Group**

Participants randomized to usual care will complete questionnaires including a depression screen, a dietary assessment, a cognitive screen, and a sleep apnea screen prior to discharge. A summary of the assessments will be given to the patient and they will be instructed to follow-up with their PCP and to monitor their BP. They will be contacted by the discharge nurse navigator or social worker at 72 hours to as per usual care to determine if they have received their medication and made their appointments. They will be offered a standard of care hospital follow up appointment with a stroke neurologist or nurse practitioner at the clinic. The RC will contact participants at 30-days, 90-days, 150-days to encourage continued participation. The RC will complete a telephone CRFs to obtain information about readmissions, hospital visits, and recurrent vascular events at 30 days and 90 days. Final outcome assessments (detailed below) will occur at 6 months.

#### **Weekend and Holiday Discharges (Both Groups)**

Eligible patients may be consented during the week but subsequently discharged on a weekend or holiday when study staff are not available to deliver equipment or provide counseling. Patients will be randomized on the day of discharge, however, if they are randomized to the intervention group, the telemonitoring equipment will be sent to them (in person or via Fedex) on the first business day after discharge. The pharmacist will provide counseling about discharge medications on the first business day after discharge. The nurse navigator or social worker call will take place at 72 hours after discharge as per usual.

## **Variables and Outcome Assessment**

Baseline demographic and clinical characteristics will be abstracted from inpatient charts, supplemented by a study CRF collected prior to randomization. Demographic variables will include age, sex, self-reported race, self-reported ethnicity, level of education, household income, insurance status, and marital status. Clinical variables will include stroke subtype, stroke etiology, prior stroke or TIA, treatment with IV tPA, endovascular therapy, admission National Institutes of Health Stroke Score, pre-stroke modified Rankin scale, presence of stroke risk factors (hypertension, diabetes mellitus, tobacco use, hyperlipidemia, obstructive sleep apnea, atrial fibrillation, coronary artery disease, systolic heart failure, substance abuse) other medical co-morbidities (obesity, chronic kidney disease), Barthel Index at baseline, Body Mass Index (BMI) at discharge, and the number of BP medications at discharge. Psychological, cognitive, and behavioral variables will include depression (Patient Health Questionnaire-9); anxiety (Generalized Anxiety Disorder-7); cognitive impairment (Montreal Cognitive Assessment), self-efficacy (Medication Adherence Self-Efficacy Scale - MASES); medication adherence (Morisky Medication Adherence Scale - MMAS); and social support (Stroke Social Network Scale).

## **Primary Clinical Outcomes**

The primary clinical outcome will be the daytime ambulatory systolic blood pressure at 6 months. Secondary clinical outcomes will include the following: daytime ambulatory diastolic blood pressure, nighttime ambulatory systolic and diastolic blood pressure; BMI at 6 months; recurrent vascular event rate (stroke, myocardial infarction, acute cardiac death); and acute healthcare utilization rate (hospital readmission and acute care visits to emergency room and/or urgent care). The 6- month behavioral outcomes will include change in self-efficacy for taking medication as prescribed, medication adherence, and caregiver burden. Patient satisfaction will be assessed using scores obtained from the Patient Telemedicine Satisfaction Survey.

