## Study Procedures:

## Eligibility Criteria

Ischemic and hemorrhagic stroke patients (N=100) identified as potentially eligible by the checklist (at least one of the following high risk criteria: uninsured, Medicaid payer status, small vessel ischemic stroke, hypertensive ICH, planning on discharging on  $\geq 2$  hypertension medications) will be eligible if they also meet the following inclusion criteria: age  $\geq 18$ ; presence of hypertension (by clinical history or hospital BP  $\geq 130/80$  mmHg on two occasions); plan to discharge home after stroke; ability to provide consent (patient or caregiver); ability to communicate in English. Exclusion criteria will include modified Rankin scale  $> 4$  at the time of enrollment (severe disability), life expectancy  $< 1$  year or terminal illness, eGFR  $< 30$  at time of discharge, pregnancy, symptomatic flow limiting carotid stenosis without plan for intervention; urine toxicology positive for cocaine or methamphetamine or history of use; long-term BP goal  $\geq 130/80$  mmHg according to clinical team; and inability to comply with study procedures \* (severe expressive language impairment, deafness, blindness, or other physical; cognitive; or social issues limiting ability to adhere to procedures).

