## Screening and Randomization

Sequential eligible patients will be approached prior to discharge to assess their interest in participating in the trial. Informed consent will be obtained from patients. Caregivers will provide consent for patients with aphasia who are otherwise eligible. Baseline assessments of socioeconomic status (education and income), medication adherence, medication adherence self-efficacy, cognition, and social support will be completed prior to randomization. We will use an internet-based system to randomize patients (1:1) to intervention versus usual care using a block design with permuted blocks of 2 to 4. The randomization allocation sequence will be developed by a statistician not involved in enrollment procedures. We will stratify based on insurance status (insured vs uninsured) and race (African American vs other) to assure that groups are balanced with respect to baseline risk. Consort criteria for the design of parallel group randomized trials will be followed.

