## **Outcome Assessments**

All enrolled patients will have final 6-month outcomes either in-clinic or by home visit with the research coordinator. Final BP will be assessed using a validated ambulatory blood pressure monitor (ABPM). The patient will be fitted with the ABPM at the final visit and will receive a Fedex envelope in which to return the ABPM after 24 hours. Weight and height will be assessed for BMI. Final healthcare utilization and recurrent vascular event CRFs will be completed and behavioral outcomes will be assessed using MASES, MMAS, and the Zarit Caregiver Burden Questionnaire. Satisfaction with telehealth visits will be assessed using the Telemedicine Satisfaction Survey (intervention arm). Patients will be compensated for final study visits (\$50).

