## **Sample Size Estimation and Statistical Approach**

Sample size estimates are based on feasibility of recruitment in a 1 year study period and anticipated attrition rates, based on our experience recruiting similar patient populations. Estimates derived from the current pilot trial in the form of posterior distribution will form the basis for simulations in planning the subsequent, larger, confirmatory trial.

Descriptive statistics will characterize the proportion of randomized patients completing assessments at baseline, 7 days (intervention), 1 month (intervention), 3 months (intervention), 5-months (intervention) and 6 months (all). Tabulation of obstacles to the intervention and completion of the outcome assessments will permit appropriate revision of the intervention for the subsequent, larger confirmatory trial. Descriptive statistics will characterize scores on the Telemedicine Satisfaction Questionnaire. Inspection of patterns of patient responses to specific

IRB NUMBER: HSC-MS-18-0925

items will permit modification of the telemedicine approach for the subsequent, larger, confirmatory trial. Generalized linear modeling will evaluate the primary clinical outcome difference in ambulatory daytime systolic BP between the two groups 6 months post-discharge as a function of treatment, race, the interaction of treatment and race, the interaction of insurance status and race. Secondary analyses will evaluate nighttime systolic, and daytime and nighttime diastolic ambulatory BP, BMI, recurrent vascular event rate, acute healthcare utilization rate, self-efficacy, medication adherence, and caregiver burden.

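### The behavioral outcomes are worded as change, yet no baseline Zarit score is planned and no use of the baseline MASES and MMAS scores in the analysis is stated

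*Combined protocol and SAP*

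**What the plan says.** All references are to the combined protocol and SAP.

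- **Primary Clinical Outcomes** lists the 6-month behavioral outcomes as "change in self-efficacy for taking medication as prescribed, medication adherence, and caregiver burden".
- **Screening and Randomization** fixes what is measured beforehand: "Baseline assessments of socioeconomic status (education and income), medication adherence, medication adherence self-efficacy, cognition, and social support will be completed prior to randomization". Caregiver burden is not in that list.
- **Variables and Outcome Assessment** names the instruments. MASES is given for self-efficacy, and the list ends with "medication adherence (Morisky Medication Adherence Scale - MMAS); and social support (Stroke Social Network Scale". The Zarit scale is absent.
- **Intervention** and **Usual Care (Control) Group** describe the pre-discharge questionnaires as "a depression screen, a dietary assessment, a cognitive screen, and a sleep apnea screen prior to discharge". None is a caregiver measure.
- **Outcome Assessments**, at the 6-month visit, says "behavioral outcomes will be assessed using MASES, MMAS, and the Zarit Caregiver Burden Questionnaire". This is the only mention of the Zarit scale.
- **Sample Size Estimation and Statistical Approach** includes in its secondary analyses "acute healthcare utilization rate, self-efficacy, medication adherence, and caregiver burden". The word *change* does not appear there. No model, covariate or baseline handling is given for these outcomes.

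**The concern.** Two things do not fit together. First, the outcome wording places caregiver burden in a list that opens with *change in*, but the schedule gives that measure no starting value. Second, the trial collects baseline MASES and MMAS from everyone, but the analysis section does not say how these scores will be used. A reader who takes the outcome wording literally would subtract baseline from the 6-month score and compare the differences between arms, which makes poorer use of the baseline data than adjustment does.

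The stakes are modest but real. Aim 2a of this pilot is to judge whether the outcome measures suit a larger trial. An outcome that can be read either as a 6-month score or as a change leaves that choice open until the data are seen. With 50 patients per arm there is little precision to spare.

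**Working it through.** **Step 1. Schedule by instrument.** The plan states no power, effect size or standard deviation for these outcomes, so there is no figure of its own to reproduce. The check sets the sections side by side.

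| Outcome | Instrument | Before randomization | 6 months | Change computable? |
|---|---|---|---|---|
| Self-efficacy | MASES | Yes | Yes | Yes |
| Medication adherence | MMAS | Yes | Yes | Yes |
| Caregiver burden | Zarit | Not listed | Yes | No; the 6-month score is available |

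**Step 2. Scope of *change in*.** The phrase certainly governs self-efficacy. It may or may not govern the other two items. On the wider reading, caregiver burden is a change outcome without a baseline. On the narrow reading, adherence and burden are 6-month scores, and adherence is treated differently from self-efficacy although both follow the same schedule. The analysis section does not settle this. It omits *change* for caregiver burden, but also for self-efficacy, which is a change outcome on either reading.

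**Step 3. Precision for MASES and MMAS.** Let s² be the variance of the score, taken as equal at baseline and 6 months, and rho the correlation between the two. Both the equal variances and rho are assumptions, since the documents give neither. Per patient, within arm:

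- Unadjusted change: 2s²(1 − rho)
- 6-month score adjusted for baseline: s²(1 − rho²)
- 6-month score alone: s²

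Change relative to adjusted: 2(1 − rho)/(1 − rho²) = 2/(1 + rho).

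| rho (assumed) | Change ÷ adjusted | Equivalent sample lost, 1 − (1 + rho)/2 | Change ÷ 6-month score alone, 2(1 − rho) |
|---|---|---|---|
| 0.4 | 2/1.4 = 1.43 | 1 − 0.70 = 30% | 1.20 |
| 0.5 | 2/1.5 = 1.33 | 1 − 0.75 = 25% | 1.00 |
| 0.6 | 2/1.6 = 1.25 | 1 − 0.80 = 20% | 0.80 |

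With 50 per arm and before attrition, unadjusted change would carry the information of about 35 per arm (50 × 0.70) at rho = 0.4 and 40 per arm (50 × 0.80) at rho = 0.6, each analyzed with adjustment. Below rho = 0.5, unadjusted change is noisier than ignoring the baseline altogether.

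**Step 4. When the loss does not arise.** Write Y for the 6-month score, X for baseline and T for arm. The model Y − X = a + bT + cX is the same as Y = a + bT + (c + 1)X. The treatment estimate b and its standard error are identical. The loss in step 3 therefore applies only if change is analyzed without baseline as a covariate.

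**Step 5. Does baseline adherence apply to everyone?** Eligibility Criteria accept "presence of hypertension (by clinical history or hospital BP" above a threshold on two occasions, so a patient may enter without an earlier hypertension diagnosis. The documents do not say which medicines the baseline MMAS and MASES refer to, how many patients took none before the stroke, or how such patients would be scored. No rule drops anyone.

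**The case against.** The strongest reply is that the sections agree if *change in* attaches only to self-efficacy. Caregiver burden is then a 6-month score compared between randomized arms, as the schedule and the analysis list allow, and the missing baseline is itself evidence for that reading. This stands as a possible reading. It does not remove the need to choose, because the text supports both.

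Three stronger readings are tempting, and the documents do not support them.

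- *Caregiver burden cannot be computed.* Only a change score cannot. Randomization makes a comparison of 6-month Zarit scores valid without a baseline.
- *The plan loses 20% to 30% of its information on MASES and MMAS.* The plan names no model for these outcomes. The loss depends on an unadjusted analysis and on an assumed rho, and modeling change with baseline as a covariate would avoid it entirely.
- *Change in adherence would rest on a selected subset because newly diagnosed patients have no baseline.* Baseline adherence and self-efficacy are planned for all patients. Those with newly found hypertension may already take other medicines; the baseline variables include diabetes, hyperlipidemia, atrial fibrillation and coronary disease. This is a possible limitation, not a demonstrated loss.

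It is also fair to say that these are secondary outcomes in a 100-patient pilot sized on feasibility.

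**Conclusion.** The point holds in a limited form. No baseline Zarit score is planned, so if *change* covers the whole list, the caregiver-burden outcome cannot be produced as worded. For self-efficacy, which is explicitly a change outcome, and for adherence, which is one on the wider reading, the baseline scores are collected but no adjustment for them is stated. If the analysis used unadjusted change, the variance would be 1.43 to 1.25 times that of the adjusted comparison. This range assumes rho of 0.4 to 0.6, equal variances at the two times, and no baseline covariate. The primary outcome, daytime ambulatory systolic pressure at 6 months, is not affected.

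**What to change.** In Primary Clinical Outcomes and in Sample Size Estimation and Statistical Approach:

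1. Define self-efficacy and adherence as the 6-month MASES and MMAS scores, compared between arms with the patient's own baseline score as a covariate.
2. Define caregiver burden as the 6-month Zarit score compared between arms, with no change score, and report by arm how many Zarit forms were completed.

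Both are wording changes that use data already planned. The cost is that caregiver burden is reported as a difference in level between arms, not as a change within caregivers. If change in burden is truly wanted, a baseline Zarit must be added, which means one more questionnaire before randomization.

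Two optional refinements need data that Variables and Outcome Assessment does not list. An indicator for patients on no medication before the stroke needs one extra chart item, because only the number of BP medicines at discharge is recorded. Restricting the Zarit comparison to patients with a caregiver needs caregiver status, preferably recorded before randomization. Status taken at 6 months could differ by arm and would bias the comparison.

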## **Outcome Assessments**

All enrolled patients will have final 6-month outcomes either in-clinic or by home visit with the research coordinator. Final BP will be assessed using a validated ambulatory blood pressure monitor (ABPM). The patient will be fitted with the ABPM at the final visit and will receive a Fedex envelope in which to return the ABPM after 24 hours. Weight and height will be assessed for BMI. Final healthcare utilization and recurrent vascular event CRFs will be completed and behavioral outcomes will be assessed using MASES, MMAS, and the Zarit Caregiver Burden Questionnaire. Satisfaction with telehealth visits will be assessed using the Telemedicine Satisfaction Survey (intervention arm). Patients will be compensated for final study visits (\$50).

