Participants will be prompted to transmit BP logs through the telemonitoring device every 2 weeks until average BP is < 130/80, then monthly thereafter. Uncontrolled BP will prompt a call from the pharmacist to discuss medication adherence and the need for further titration. Subsequent video telehealth visits for intervention patients will be attended by the NP (or MD) and pharmacist 1 month, 3 months, and 5 months after enrollment. Care plans will be reviewed and medication and lifestyle adherence will be assessed. Medications will be adjusted as appropriate. Participants will complete electronic health care utilization and recurrent vascular CRFs using the iPad at 3 months and 6 months (final outcome). Participants will receive educational messaging once every other week throughout the study period. Messages will be sent to the participants' cellular phones. The messages will contain one of the following: a reminder to monitor BP, information from about lifestyle and diet for BP reduction, or a message from the pharmacist about medication adherence. Final outcome assessments (detailed below) will occur at 6 months.

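### The 6-month self-report outcomes are collected by a coordinator role that very likely knows the arm, and utilization and event data are collected differently in the two arms

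*Combined protocol and SAP*

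**What the plan says.** **Final assessment, both arms** (Outcome Assessments): "All enrolled patients will have final 6-month outcomes either in-clinic or by home visit with the research coordinator". At this assessment "behavioral outcomes will be assessed using MASES, MMAS, and the Zarit Caregiver Burden Questionnaire". Whether these are interviewed or self-completed is not stated. For one arm there is a further form: "Satisfaction with telehealth visits will be assessed using the Telemedicine Satisfaction Survey (intervention arm".

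**Contact during follow-up.** In usual care (Usual Care (Control) Group): "The RC will contact participants at 30-days, 90-days, 150-days to encourage continued participation". In the intervention arm (Intervention): "Subsequent video telehealth visits for intervention patients will be attended by the NP (or MD) and pharmacist 1 month, 3 months, and 5 months". That section also describes pharmacist calls and educational messages, but no coordinator calls.

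**Utilization and vascular events.** In usual care: "The RC will complete a telephone CRFs to obtain information about readmissions, hospital visits, and recurrent vascular events at 30 days and 90 days". In the intervention arm: "Participants will complete electronic health care utilization and recurrent vascular CRFs using the iPad at 3 months and 6 months (final outcome". For the final assessment, Outcome Assessments adds only: "Final healthcare utilization and recurrent vascular event CRFs will be completed". It does not say by whom or how.

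**Analysis.** Sample Size Estimation and Statistical Approach lists self-efficacy, medication adherence, caregiver burden, utilization and recurrent events as secondary analyses, and describes the satisfaction scores descriptively. Primary Clinical Outcomes names daytime ambulatory systolic pressure as primary.

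**The concern.** MMAS, MASES and Zarit are answered by patients or caregivers, at a visit run by a role that has an arm-specific history with half of them. If the collector knows the arm, the way items are introduced, explained or probed can differ between arms, and answers can shift without any change in behavior. The intervention works on the very content that MMAS and MASES measure, through adherence review at video visits, pharmacist calls and messages, so these answers are easily swayed.

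Baseline adherence and self-efficacy are taken before randomization (Screening and Randomization). An arm-related shift arising only at 6 months is therefore not cancelled by taking change from baseline; it falls on the between-arm difference. At stake are the planned secondary comparisons, and Aim 2a's purpose of examining whether the measures suit a larger trial.

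For utilization and events the issue is different. The arms report through different channels at different times, so counts may differ because of how they were obtained.

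**Working it through.** The sample size of 50 + 50 = 100 rests on feasibility, with no alpha, power, SD or effect size, so the plan has no figure on this point to reproduce. The check is a comparison of sections plus one illustration.

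**1. Does the collector know the arm?**
- The coordinator role contacts usual-care patients three times (Usual Care (Control) Group). No such contact appears under Intervention.
- The same role conducts the 6-month visit for everyone (Outcome Assessments).
- No section provides for a masked assessor, separates follow-up contact from assessment, or conceals the arm at the visit.
- The satisfaction survey exists for one arm only, so whoever hands it over learns the arm.

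Knowledge of the arm is thus a strong inference, not a stated fact. The documents name a role, and the front matter has more than one entry under Research Coordinator.

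**2. Which outcomes are exposed?**
- MMAS, MASES and Zarit: self-reported, compared between arms, mode unstated. Exposed.
- Ambulatory pressure: recorded by a worn device. Largely protected.
- Satisfaction: intervention arm only and descriptive. A score could be flattering, but there is no treatment comparison to bias.

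**3. Utilization and events, side by side**

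| | Usual care | Intervention |
|---|---|---|
| Interim mode | Coordinator by telephone | Self-completed on iPad |
| Interim times | 30 and 90 days | 3 months |
| 6-month mode | Not stated | iPad (Intervention); not stated (Outcome Assessments) |

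Usual care thus has two interim reports and the intervention arm one. No recall period is given for any form.

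**4. Illustration of size.** Assumptions, none from the documents: two-sided alpha 0.05, no true effect, reporting in one arm shifted by b SD in either direction, and n evaluable per arm (50 if nobody is lost, 40 as a lower case).

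SE of the standardized difference = sqrt(2/n). P(nominal significance) = Φ(b/SE − 1.96) + Φ(−b/SE − 1.96).

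- n = 40: SE = sqrt(2/40) = 0.224. For b = 0.2, b/SE = 0.894 and P = 0.145. For b = 0.3, b/SE = 1.342 and P = 0.269.
- n = 50: SE = sqrt(2/50) = 0.200. For b = 0.2, b/SE = 1.0 and P = 0.170. For b = 0.3, b/SE = 1.5 and P = 0.323.
- Smaller and larger shifts: b = 0.1 gives 0.073 (n = 40) and 0.079 (n = 50); b = 0.5 gives 0.609 and 0.705.

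With b = 0 the value is 0.05 for either n.

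**The case against.** The strongest reply has five parts.

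- **Mode.** The plan does not say the coordinator interviews anyone. Patients complete questionnaires before discharge, and self-completion at 6 months may already be the intention. This stands: what is shown is an unspecified mode with an unmasked collector present, not biased interviewing.
- **Mechanism and direction.** Participants know they had telehealth, and masking the collector cannot change that. The coaching is done by the nurse practitioner or physician and the pharmacist, while the coordinator's rapport is with usual-care patients, so the two influences could pull in opposite directions. This stands, and it is why no direction is claimed and why any remedy is partial.
- **Importance.** Aim 2a judges suitability by completion and barriers, and Aim 2c estimates the effect on ambulatory systolic pressure. The documents do not say that MMAS or MASES differences will decide which measures go forward. This lowers the stakes, but the behavioral comparisons are still planned analyses.
- **Magnitude.** The shift, the alpha and the evaluable number are all assumed. Zarit also needs a caregiver, so 40 per arm may be too many for it. Both points stand.
- **Practicality.** Only intervention patients are supplied with an iPad, and patients with aphasia can be enrolled, so devices and help with completion must be planned for.

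A reader might also infer that the coordinator takes utilization and event data face to face in both arms. The Intervention section contradicts that for its own arm. A reader might suppose that most final visits are at home; the plan gives clinic or home, with no frequency.

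**Conclusion.** The concern holds in limited form. One role makes the follow-up contacts in usual care only and then conducts the 6-month visit in both arms. No masking is described, and an arm-specific survey is part of that assessment. Collector influence on the between-arm comparisons of MMAS, MASES and Zarit is therefore a real risk that the plan does not address. Its size and direction are unknown. The 15% to 27% range shows what a modest shift could do with 40 per arm; it does not estimate this trial's error rate.

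Separately, the utilization and event data differ by arm in mode and interim schedule, and the 6-month mode is left open between Intervention and Outcome Assessments.

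Two stronger readings are not supported. The primary result is not put in doubt, because ambulatory pressure is device-recorded. Satisfaction cannot yield a biased treatment difference, because it has no comparator. This is a cheap improvement to secondary and behavioral outcomes in a pilot, not a flaw in its main estimate.

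**What to change.** 1. In both arms, have patients or caregivers self-complete MASES, MMAS and Zarit at the start of the 6-month visit, before any coordinator interview, in the same order and on the same form. Use a study tablet or paper, since usual-care patients are not given an iPad. Use the same mode for MASES and MMAS at baseline, because change is analysed.
2. Give the satisfaction survey last, self-completed, so that it cannot disclose the arm before the compared instruments are done.
3. Where help is needed, for example with aphasia, use a fixed script and record that help was given.
4. Reconcile Intervention, Usual Care (Control) Group and Outcome Assessments so that utilization and event forms use one mode and the same time points in both arms.

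Cost: procedure wording, form set-up and a shared tablet or paper forms; no extra staff. Some patients will need help. Reporting bias from participants who know their arm is reduced, not removed.
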